12.5 Patient Confidentiality

The Sponsor of this study will maintain the highest confidentiality standards, ensuring patient's anonymity and protecting their identities from unauthorised parties. Through this study, each patient will be identified through the assignment of a unique identification number (i.e. Patient ID) on all study documents and electronic databases. All study-related documents will be securely stored and accessible only by the Investigator, the study staff, and authorised personnel. No personal detail will be included in any data transmitted to the Sponsor.

Any medical information pertaining to the patients is considered confidential and may be only disclosed to third parties as permitted by the ICF, once dated, and signed by the patient.

12.6 Data Protection

Before any data can be collected in the context of this trial, all patients must provide all pertinent authorisations, as per local or national law. Additionally, each patient will be informed about their rights regarding access, objection and correction to any of their data recorded during the course of the study. Every database is GDPR compliant.

12.7 Financing and Insurance

The Sponsor is financially responsible for the conduct of the study.

The Sponsor has an insurance policy for the duration of the study, covering subjects and Investigators in respect to the risks involved in conducting this study according to this clinical investigational plan. The insurance policy can be made available to the Investigator and the EC upon request.

13 STUDY PERSONNEL AND ADMINISTRATIVE STRUCTURE

The Sponsor of this trial is FeetMe. Six study centres will participate in this study to recruit approximately 150 patients. The Sponsor will be responsible for data management, statistical analysis and medical oversight.

A contract research organisation (CRO) will be contracted and will be responsible for the administrative aspects of the study. This includes but is not limited to: initiation of the study, management and monitoring of the study and data monitoring.

14 APPENDICES

14.1 Appendix A – Rehabilitation Exercises

During the static exercises the phone should be positioned at eye level and an object to provide the patient with support should be placed nearby (e.g.: a chair to hold on to). For the dynamic exercises the patient should keep the phone in their pocket.

14.1.1 Static Exercises

14.1.1.1 Balance

Support Transfer

The objective of this exercise is to improve multi directional support transfer. The task is to catch the targets appearing on the screen by moving the centre of gravity without moving the feet on the ground. The patient should reach the highest number of targets during the allocated time. The exercise has six difficulty levels across which the amplitude of the movement required to reach a target increases and the directions of the transfer support needed become more complex. The biofeedback given includes the total number of targets reached and the percentage of success.

Stabilization

The objective of this exercise is to reinforce balance by working on stabilising the body. The task is to catch the targets appearing on the screen by moving the centre of gravity without moving the feet on the ground and then to maintain the position for 5 to 7s until the object disappears and repeat this as many times as possible during the allocated time. The exercise has six difficulty levels across which the amplitude of the movement required to reach a target increases and the directions of the transfer support needed become more complex. The biofeedback given includes the total number of targets on which the patient stabilized and the percentage of success.

Balance and speed

The objective of this exercise is to improve the speed of transfer support to facilitate daily activities. The task is to catch the targets appearing on the screen as quick as possible by moving the centre of gravity without moving the feet on the ground. Targets that are not reached within 5 seconds will automatically disappear and will be regenerated somewhere else. The patient should reach the highest number of targets during the allocated time. The exercise has six difficulty levels across which the amplitude of the movement required to reach a target increases and the directions of the transfer support needed become more complex. The biofeedback given includes the total number of targets reached and the percentage of success.

14.1.1.2 Muscle strengthening

Plantar flexion

The objective of this exercise is to reinforce the lower limbs to facilitate balance and walking. The task is to move the centre of gravity forward towards the toes from a position of having both feet flat on the ground to lifting the heels off. A gauge is displayed on the screen during the exercise and the patient should fill the gauge as much as possible. Each time the patient puts more than 85% of their weight on the front sensors of the insoles the plantar flexion is indicated as done. The biofeedback given includes the total number of movements completed and the percentage of success.

Sit to Stand

The objective of this exercise is to reinforce muscle strength and improve postural symmetry. The task is to stand up from sitting position and sit back down completely with equally distributed body weight on both feet. The patient should complete as many sit to stand rounds as possible during the time allocated. The biofeedback given includes the total number of rounds correctly performed and the distribution of the pressure on each leg.

14.1.2 Dynamic Exercises

14.1.2.1 Gait Quality

Big Step

The objective of this exercise is to improve balance and walking. The task is to walk with the longest possible stride length. Prior to the task the patient needs to perform a thirty second comfortable walk to set the baseline for the evaluation of success and to serve as a basis for recalibrating the difficulty level by assessing their natural stride length. A stride is considered successful if it is at least fifteen percent longer than the average natural step. As the patient improves their gait quality throughout the program they will need to keep doing better compared to their actual status. The biofeedback given includes the percentage of success that is calculated in comparison to the patient's regular stride length using a specific formula.

Step Sequence

The objective of this exercise is to improve gait quality. The task is to preform steps which follow the sequence of heel-strike – full contact with the ground – toe-off (propulsion). If any of the components of the sequence is missing it will not be counted. The biofeedback given is the percentage of success for the left and right foot separately.

14.1.2.2 Endurance

Rhythmic Stimulation

The objective of this exercise is to improve the velocity and to regulate cadence. The task is to follow the pace of a metronome. Prior to the task the patient needs to perform a thirty second comfortable walk to set the baseline for the evaluation of success and to serve as a basis for recalibrating the difficulty level by assessing the natural cadence. The metronome is set to a pace ten percent higher than assessed during this regular walk. The biofeedback given includes the percentage of success and the reached cadence versus the target one.

Heel Strike

The objective of this exercise is to improve gait quality and endurance. The task is the same as during the Step Sequence (walk at a normal pace starting each step with a heel strike and finishing with toeoff), only for a longer duration. Therefor, an additional objective of this task is to assess whether gait quality decreases over time.

Free Walking

The objective of this exercise is to improve endurance and to assess gait evolution by all the spatiotemporal and pressure parameters. The patient will need to perform comfortable pace walking for the duration defined in their allocated program (e.g.: sixty minutes per week). Patients can distribute the total time to be completed at their convenience. CIP Number 2023-A00150-45 Final version 0.2

14.2 Appendix B – Rehabilitation Program

14.2.1 Decision Tree for Initial Program

CIP Number 2023-A00150-45 Final version 0.2

14.2.2 Program Adaptation Principles

14.2.3 Program A

Periods	Nb sessions	Duration of sessions	Free walking ⁄ week	Total weekly time	
W1-W3	4x/week	30min	60min	=3h	
W4-W6	4x/week	45min	60min	=4h	
W7-W9	4x/week	60 min	60min	=5h	
W10-W12	4x/week	60 min	60min	=5h	Intens level
W12-W24 (if the patient pursues)	4x/week	60 min	60min	=5h	

14.2.4 Program B

Periods	Nb sessions	Duration of sessions	Free walking ⁄ week	Total weekly time	
W1-W3	3x/week	30min	60 min	=2h30	
W4-W6	4x/week	30min	60 min	=3h	
W7-W9	4x/week	45min	60 min	=4h	
W10-W12	4x/week	60min	60 min	=5h	Intensity level
W12-W24 (if the patient pursues)	4x/week	60 min	60 min	=5h	

14.2.5 Program C

Periods	Nb sessions	Duration of sessions	Free walking ⁄ week	Total weekly time	
W1-W3	3x/week	30min	30min	=2h	
W4-W6	4x/week	30min	30min	=2h3o	
W7-W9	4x∕week	45min	30min	=3h3o	
W10-W12	4x∕week	60min	30min	=4h3o	Intensity level
W12-W24 (if the patient pursues)	4x/week	60min	30 min	=4h3o	

14.3 Appendix C – FeetMe Satisfaction Questionnaire for Initial Patient Training

A compléter après la formation initiale.

1) Le temps de formation était-il suffisant ?

- o Oui complètement
- o Plutôt oui
- o Je ne sais pas
- Plutôt non
- o Non pas du tout

2) Suite à la formation initiale, vous êtes-vous senti en confiance concernant l'utilisation du dispositif ?

- Oui complètement
- Plutôt oui
- Je ne sais pas
- o Plutôt non
- o Non pas du tout

3) Le format par visio-conférence de la formation était-il satisfaisant ?

- o Oui complètement
- o Plutôt oui
- \circ Je ne sais pas
- o Plutôt non
- o Non pas du tout

4) Les informations communiquées lors de la formation initiale ont-elles été claires ?

- o Oui complètement
- o Plutôt oui
- \circ Je ne sais pas
- Plutôt non
- o Non pas du tout

5) Sur une échelle de 0 à 10, quelle note donneriez-vous à cette formation initiale ?

6) Selon vous, comment pourrions-nous améliorer cette formation initiale ?

14.4 Appendix D – FeetMe Satisfaction Questionnaire – Patient Version

A compléter à Visite 3 et à Visite 4, si applicable.

Questions spécifiques au programme

1) Les objectifs du programme sont-ils en accord avec mes objectifs personnels (ex: sortir en autonomie pour faire des courses ou bien se promener) ?

- Tout à fait d'accord
- o D'accord
- Pas d'avis
- o Pas d'accord
- Pas du tout d'accord

2) Quelle est pour vous la valeur ajoutée de FeetMe Rehabilitation dans votre vie quotidienne ? (plusieurs réponses possibles)

- Exercices personnalisés
- Je peux pratiquer quand et où je veux
- o Un suivi téléphonique régulier personnalisé
- Éviter les déplacements
- o Me permet de pratiquer davantage
- Me motive
- Non applicable
- \circ Autre :

3) Lorsque vous utilisez FeetMe Rehabilitation, vous sentez-vous en sécurité lors de la réalisation des exercices ?

- o Tout à fait d'accord
- o D'accord
- o Pas d'avis
- Pas d'accord
- Pas du tout d'accord

4) Quel est votre niveau de satisfaction en ce qui concerne le suivi ?

- o Très satisfait
- Plutôt satisfait
- Ni satisfait, ni insatisfait
- Plutôt insatisfait
- Insatisfait

5) Si vous deviez changer quoi que ce soit concernant le suivi, qu'est ce que ce serait ? (ex: la fréquence, la durée, le contenu..)

6) Quel est votre niveau de satisfaction concernant votre relation avec l'APA en charge de votre suivi ?

- o Très satisfait
- o Plutôt satisfait
- o Ni satisfait, ni insatisfait
- Plutôt insatisfait
- o Insatisfait

7) Parmi les propositions suivantes, quel moyen de rééducation préférez-vous ?

- Rééducation à domicile
- Rééducation chez le kinésithérapeute
- Une combinaison des deux
- Non applicable

8)Recommanderiez-vous la solution à quelqu'un qui se trouve dans la même situation que vous ?

- o Très probablement
- Probablement
- Je ne sais pas
- Probablement pas
- Très probablement pas

Questions spécifiques au matériel

1) Quel est votre niveau de satisfaction en ce qui concerne l'utilisation de la solution FeetMe Rehabiltation ? (semelles, application, chargeur)

- Très satisfait
- Plutôt satisfait
- o Ni satisfait, ni insatisfait
- o Plutôt insatisfait
- o Insatisfait

2) Quel est votre niveau de satisfaction en ce qui concerne l'utilisation des semelles FeetMe (confort, utilisation...)

- Très satisfait
- Plutôt satisfait
- Ni satisfait, ni insatisfait
- Plutôt insatisfait
- o Insatisfait

3) Si vous pouviez changer quoi que ce soit sur les semelles FeetMe Monitor, qu'est ce que ce serait ? (ex: matériau, couleur, forme, chargeur, etc)?

4) Si vous pouviez changer quoi que ce soit concernant l'application FeetMe rehabilitation, qu'est ce que ce serait ? (ex: interface, retour en temps réel, menu, etc...) ?

5) Avez-vous rencontré des difficultés lors de l'utilisation ? Si oui, lesquelles ?

6) Quel est votre niveau de satisfaction concernant l'assistance technique ?

- Très satisfait
- Plutôt satisfait
- o Ni satisfait, ni insatisfait
- Plutôt insatisfait
- o Insatisfait

14.5 Appendix E – Satisfaction Questionnaire – Investigator Version

A compléter à la fin de l'étude.

- 14.5.1 Application FeetMe Evaluation application et semelles FeetMe Monitor
 - 1. Comment trouvez-vous l'utilisation de la solution ?
- Très simple d'utilisation
- Plutôt facile d'utilisation
- Ni facile ni difficile d'utilisation
- Plutôt difficile d'utilisation
- Très difficile à utiliser

2. A quelle fréquence intégrez-vous l'utilisation de la solution dans votre pratique quotidienne ?

- Très souvent
- Souvent
- Neutre
- Pas souvent
- Rarement

3. Pour quelle raison implémentiez-vous cette solution ?

- Expliquer certaines choses et faire des retours aux patients
- Suivre l'évolution de l'avancée de la maladie
- Guider la rééducation ou le traitement
- Autre :
- D NA
 - De 0 à 10, dans quelle mesure êtes-vous susceptible de recommander la solution FeetMe Evaluation à vos collègues ? (0: je ne recommande pas FeetMe, 10: je recommande absolument)

.....

- 5. Quel est votre niveau de satisfaction concernant la qualité des semelles FeetMe Monitor ?
- Très satisfait
- Plutôt satisfait
- Ni satisfait, ni insatisfait
- Plutôt insatisfait
- Insatisfait
 - 6. Quel est votre niveau de satisfaction concernant la qualité des de l'application FeetMe Evaluation ?
- Très satisfait
- Plutôt satisfait
- Ni satisfait, ni insatisfait
- Plutôt insatisfait
- Insatisfait
 - Si vous pouviez changer quelque chose sur l'application FeetMe Evaluation, qu'est-ce que ce serait ? (ex : interface, menu, etc)?

8. Si vous pouviez changer quelque chose sur les semelles FeetMe Minitor, qu'est-ce que ce serait

- Si vous pouviez changer queique chose sur les semenes reetivie Minitor, qu'est-ce que ce serait (ex.: matière, couleur, forme, mode de chargement, etc)?
- - 9. Avez-vous rencontré des difficultés ? Si oui précisez lesquelles

CIP Number 2023-A00150-45 Final version 0.2

10. Quel est votre niveau de satisfaction concernant le support technique ?

- Très satisfait
- Plutôt satisfait
- Ni satisfait, ni insatisfait
- Plutôt insatisfait
- Insatisfait

FeetMe Rehabilitation

- 1. Quel a été le niveau de satisfaction de vos patients le programme FeetMe Rehabilitation ?
- Très satisfait
- Plutôt satisfait
- Ni satisfait, ni insatisfait
- Plutôt insatisfait
- Insatisfait
 - Avez-vous observé une amélioration globale des patients grâce à FeetMe Rehabilitation? (Oui/Non)

2. Comment les patients dans le groupe FeetMe Rehabilitation se comparent-ils aux patients dans le groupe kinésithérapie conventionnelle en termes de progression ?

- Beaucoup plus de progrès
- Plus de progrès
- Identique
- Moins de progrès
- Beaucoup moins de progrès

Veuillez expliquer pourquoi selon vous :

 De 0 à 10, dans quelle mesure êtes-vous susceptible de recommander la solution FeetMe Rehabilitation à vos collègues ? (0: je ne recommande pas FeetMe, 10: je recommande absolument)

4. Si la solution était remboursée, quelle serait la probabilité que vous la proposeriez à vos patients ?

- Très souvent
- Souvent
- Neutre
- Pas souvent
- Rarement

6. Quel est votre niveau de satisfaction concernant la solution Rehabilitation ? (ex: interface, retour en temps réel, programme, plateforme web, etc)?

Très satisfait

- Plutôt satisfait
- D Ni satisfait, ni insatisfait
- Plutôt insatisfait
- Insatisfait

7. Si vous pouviez changer quelque chose sur la solution FeetMe Rehabilitation, qu'est-ce que ce serait (ex: composition des exercices, l'interface, les retours en temps réel, le menu, etc?)

.....

8. Si vous pouviez changer quelque chose sur les programmes, qu'est-ce que ce serait (ex : fréquence des séances, les règles d'adaptation, la fréquence des suivis, etc...)

.....

14.6 Appendix F – Conventional Physiotherapy Tracking Sheet

A remplir tout au long de la durée de l'étude.

ID Patient:		
Date de la séance (DD/MM/YY)	Durée de la séance (heure)	Type d'exercice de rééducation réalisé
//		
//		
//		
//		
//		
//		
//		
//		
//		
//		
//		
//		
//		
//		
//		
//		
//		
//		
//		
//		
//		

Fiche de suivi kinésithérapie

Instructions pour compléter le formulaire

Vous devez remplir ce formulaire car vous suivez une rééducation conventionnelle chez un kinésithérapeute. Nous vous demandons de garder une trace de votre traitement en l'enregistrant selon les instructions ci-dessous durant toute la durée de l'étude. Vous pouvez demander à votre kinésithérapeute de remplir le formulaire pour vous ou de vérifier les informations que vous avez renseignées. Si vous n'avez plus de place, veuillez en informer votre site pour vous fournir un nouveau formulaire.

Nous vous demandons de bien vouloir :

- mettre votre identifiant patient en haut du formulaire.
- mettre la date de votre séance de kinésithérapie dans la première colonne. Seules les séances qui ont un impact sur vos mouvements sont à renseigner. Si vous recevez un autre traitement (ex : orthophonie), il n'est pas nécessaire de remplir ce formulaire.
- mettre la durée de la séance dans la deuxième colonne.
- décrire les exercices que vous réalisez au cours de la séance.

Merci de rapporter ce formulaire lors de vos visites en centre et de le donner à votre évaluateur.

Exemple:

Date de la séance (DD/MM/YY)	Durée de la séance (heure)	Type d'exercice de rééducation réalisé
14/04/2023	1.5	Exercices d'équilibre Entrainement endurance
21/04/2023	1	Vélo d'intérieur, étirements

14.7 Appendix G – Falls Diary

A compléter tout au long de la durée de l'étude.

Carnet de chute du patient

Identifiant / ID Patient:							
Date de l'évènement	nt Nombre Nombre de chutes de type		Nombre de	Nombre de			
(DD/MM/YY)	de chutes	Α	В	С	D	« presque chutes »	Déséquilibre rattrapé par l'aidant
//							
//							
//							
//							
//							
//							
//							
//							
//							
//							
//							
//							
//							
//							
//							
//							
//							
//							
//							
//							
//							
Guide de remplissage du carnet de chutes

Vous devez remplir ce carnet de chutes au cours de l'étude.

L'identification du carnet doit comporter :

- Le numéro de patient qui vous aura été attribué
- La date à laquelle la « chute » / « presque chute » / « déséquilibre rattrapé par l'aidant » est survenue.

Les informations attendues le jour où l'évènement est survenu sont:

- Le nombre de types de « chute » / « presque chute » / « déséquilibre rattrapé par l'aidant »
- Le nombre de chutes par gravité => seules les « chutes » sont concernées, identifier pour chacune par leur gravité : A, B, C ou D

Définition des chutes :

La chute est définie comme le fait de se retrouver involontairement sur le sol ou dans une position de niveau inférieur par rapport à sa position de départ.

La presque chute est définie comme le fait de se rattraper à un objet pour éviter de tomber ou de se rattraper spontanément sans objet.

Le Déséquilibre rattrapé par l'aidant est définie comme le fait que l'aidant intercepte le patient avant qu'il ne tombe.

Les différentes gravités de chutes sont les suivantes :

A – Blessure sérieuse : fractures enregistrées médicalement, blessure interne ou blessure de la tête nécessitant un passage aux urgences ou une hospitalisation.

B – **Blessure modérée** : Contusion, entorse, coupure, nécessitant une consultation par un professionnel médical ou de santé, examen tel que examen clinique, radiographies, sutures.

C – Blessure mineure : Contusion ou écorchure ne requérant pas l'assistance d'un professionnel, diminution des fonctions physiques (due à la douleur ou à la peur de chuter) pendant au moins trois jours.

D - Pas de blessure : Aucune blessure physique détectée.

Par exemple:

Date de l'évènement	Nombre	Nom	bre de c	hutes d	e type	Nombre de	Déséquilibre	
(DD/MM/YY)	de chutes	Α	В	С	D	« presque chutes »	rattrapé par 1'aidant	
05/03/23	1			1				
23/05/23						2		

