5 STUDY OBJECTIVES AND ENDPOINTS

Table 5.1 Study Objectives and Endpoints

Primary Objective	Primary Endpoints				
To evaluate the efficacy of FeetMe home-based rehabilitation program compared to conventional physiotherapy at Week 12 in PD patients assessed by gait velocity.	Change from baseline to Week 12 (Visit 3) in gait velocity (cm/s) assessed during the 6 Minutes Walk Test (6MWT).				
Key Secondary Objective	Key Secondary Endpoint				
To evaluate the efficacy of FeetMe home-based rehabilitation program compared to conventional physiotherapy at Week 12 in PD patients assessed by stance time variability.	Change from baseline to Week 12 (Visit 3) in Stance Time Variability assessed during the 6 Minutes Walk Test (6MWT).				
Secondary Objectives	Secondary Endpoints				
To evaluate the efficacy of FeetMe home-based rehabilitation program compared to conventional physiotherapy at Week 12 in PD patients assessed	• Rate of falls at Week 12 (Visit 3) based on the results of the falls diary.				
 by: rate of falls standard gait and balance exercises 	• Change from baseline to Week 12 (Visit 3) in the asymmetry of the swing duration assessed during the 6 Minutes Walk Test (6MWT).				
MDS-UPDRS Part IIIquality of life	• Change from baseline to Week 12 (Visit 3) in the MiniBESTest.				
	• Change from baseline to Week 12 (Visit 3) in MDS-UPDRS part III sub-score.				
	• Change from baseline to Week 12 (Visit 3) the results of the Parkinson Disease Questionnaire (PDQ-39)				
Exploratory Objectives	Exploratory Endpoints				

• To explore the long term efficacy home-based rehabilitation program to conventional physiotherapy in pa	of FeetMe compared atients who	Rate of falls at Week 24 based on the results of the falls diary. Change from Baseline to Week 24 (Visit 4)
continue to Week 24		and from Week 12 (Visit 3) to Week 24 in:
• To explore the maintenance of the 3 months in patients who stop phy at Week 12.	effect after vsiotherapy	- Gait velocity (cm/s) assessed during the 6MWT
 To explore the efficacy in patients of from one treatment to the other at X 	who switch Veek 12	- Stance Time Variability assessed during the 6MWT
	V CCR 12.	- Asymmetry of the swing duration assessed during 6MWT
		- the Mini-BESTest
		- MDS-UPDRS Part III sub-score
		- the results of the PDQ-39
	•	Change from Baseline to Week 12 (Visit 3) and to Week 24 (Visit 4) and from Week 12 to Week 24 in the:

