7.4 Primary Intervention Period

Following the Baseline Visit, all patients will begin their 12-week physiotherapy (or no-physiotherapy) regimen according to their randomisation.

During this period:

- All patients will participate in the Remote Gait Monitoring 1 and Visits 1-3 (Sections 7.3.1, 7.3.2, 7.3.3).
- Patients on the Conventional Physiotherapy arm, if they have access to it will start or continue their conventional physiotherapy and will keep track of it using the Conventional Physiotherapy Tracking Sheet (Appendix F). Patients who did not have access to CPt at the time of inclusion but manage to arrange one during the Primary Intervention Period will restart their PIP.
- On the other arm patients will start the FeetMe rehabilitation program (Section 4.4, Appendix A and B).
- In addition, all patients will keep a falls diary (Appendix G).

7.4.1 Remote Gait Monitoring 1

At the end of the Baseline Visit, all patients will take the FeetMe Insoles, mobile devices and chargers with them to their homes. A Patient User Guide will be provided.

- All patients will use the insoles remotely while performing their day-to-day activities (including physiotherapy) for two weeks. Data will be recorded in standalone mode (without a phone).
- Patients will download the data from the insoles at the end of each day.

7.4.2 Visits 1 and 2

Four and eight weeks after Baseline Visit, two remote visits (Visit 1 and 2) will take place. Patients will be asked to fill in the following questionnaires:

- PDSS-2
- Pain VAS
- Parkinson Disease Questionnaire, Short Form (PDQ-8).

7.4.3 Visit 3

Twelve weeks after Baseline Visit, that is, at the end of the 12-week Primary Intervention Period, all patients will participate in an in-clinic visit (Visit 3), where they will perform the same series of assessments as in the Baseline Visit. Patients will need to bring their FeetMe devices, their diaries, trackers and filled-in questionnaires to the visit.

The following assessments will be performed at Visit 3:

- Gait Assessments, which must be performed in the ON-phase:
 - 6 Minutes Walk Tests (6MWT)
 - Mini-BESTest.

During the 6MWT and the Mini-BESTest patients must wear the insoles. Specific instructions set out in the Site User Manual must be followed when setting up and executing the assessments.

- Disease specific rating scales:
 - MDS-UPDRS
- Other Assessments:
 - FOG-Q
 - PDSS2
 - Pain VAS
 - PDQ39

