8.7 Falls Diary

Patients have to keep a falls diary throughout their participation in the study by registering falls and near falls, as described in Appendix G. They will need to bring their diaries to the site visits so the data can be registered in the database.

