
9.5.2 Analysis for the secondary endpoints

The statistical method described for the primary objective will be used for the analysis of the following secondary endpoints:

- Change from baseline to Week 12 (Visit 3) in Stance Time Variability assessed during the 6 Minutes Walk Test (6MWT).
- Change from baseline to Week 12 (Visit 3) in the asymmetry of the swing duration assessed during the 6 Minutes Walk Test (6MWT).
- Change from baseline to Week 12 (Visit 3) in the MiniBESTest.
- Change from baseline to Week 12 (Visit 3) in MDS-UPDRS part III sub-score.
- Change from baseline to Week 12 (Visit 3) the results of the Parkinson Disease Questionnaire (PDQ-39)

The rate of falls during the primary intervention period will be compared between the 2 groups using a generalized linear model (GLM with log link function and negative binomial distribution) with the logarithm of duration of patient's follow up (censored at week 12) as offset variable. Effect size will be estimated by the relative risk ((Feetme rehabilitation versus conventional rehabilitation) and it's 95% confidence interval from the using GLM model.

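### The falls diary has no way to record a fall-free period and the falls model uses all follow-up as exposure, so an unkept diary cannot be told from an absence of falls

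*Protocol*

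**What the plan says.** Section 5 (Table 5.1) lists the falls endpoint first among the secondary endpoints: "Rate of falls at Week 12 (Visit 3) based on the results of the falls diary".

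The diary is described in two places. Section 8.7 says "Patients have to keep a falls diary throughout their participation in the study by registering falls and near falls". Appendix G gives the form and its completion guide. The date to be written is that of the event: "La date à laquelle la « chute » / « presque chute » / « déséquilibre rattrapé par l'aidant » est survenue". The details are requested for the day of the event: "Les informations attendues le jour où l'évènement est survenu sont". The form has no field for zero falls, for the period covered or for whether the diary was kept. Its worked example shows two event dates and nothing for the time between them.

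On collection, Section 8.7 says "They will need to bring their diaries to the site visits so the data can be registered in the database". Section 7.4.2 says "Four and eight weeks after Baseline Visit, two remote visits (Visit 1 and 2) will take place", and lists only three questionnaires for them (PDSS-2, pain VAS, PDQ-8). The first planned diary collection after baseline is therefore Visit 3, at Week 12.

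Section 9.5.2 analyses the falls by negative binomial regression on the log scale. Exposure enters that model as follows: "with the logarithm of duration of patient's follow up (censored at week 12) as offset variable". Section 9.5.3 repeats this model to Week 24.

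**The concern.** A count model with an exposure offset assumes that every event within the counted exposure would have been recorded. Here exposure is time in the study, while events are seen only while the patient keeps the diary. A blank stretch adds full exposure and no falls, whether the patient did not fall or did not write.

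The query process in Section 10.3 cannot find the gap, because a blank in an event-only log is not recognisable as missing. Nor can a later analysis plan recover diary coverage that the form never collected. That is why the point belongs to the protocol and its appendix and cannot be left to the statistical analysis plan.

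Two things are at stake. Falls that are left out lower the absolute rates in both arms. If they are left out more often in one arm, the rate ratio partly measures diary keeping. The second is possible here: the trial is open-label (Section 6.1), and regular calls from the adapted physical activity (APA) specialist belong to the FeetMe programme only (Section 4.4).

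**Working it through.** The protocol gives no fall rate, power or sample size for falls, so there is no stated figure to reproduce. Its sample size concerns gait velocity and does not bear on this point.

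**Inputs.** From the protocol: a log link and negative binomial distribution, with log follow-up to Week 12 as offset (9.5.2); 75 patients recruited per group (9.4). Assumed, because the protocol gives nothing: the share of follow-up in which the diary is not kept, uF in the FeetMe arm and uC in the control arm.

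**Worst-case formula.** Suppose that falls are equally frequent in kept and unkept time, and that every fall in unkept time is lost. The expected estimated rate in an arm is then (1 − u) × true rate, and

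expected rate ratio = true rate ratio × (1 − uF)/(1 − uC).

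| Assumed uF | Assumed uC | Factor | True 1.00 becomes | True 0.80 becomes |
|---|---|---|---|---|
| 20% | 20% | 0.80/0.80 = 1.00 | 1.00 | 0.80 |
| 10% | 30% | 0.90/0.70 = 1.29 | 1.29 | 1.03 |
| 30% | 10% | 0.70/0.90 = 0.78 | 0.78 | 0.62 |

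In the first row the ratio is right, but both absolute rates are 20% too low.

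**Simulation.** Setting: 75 per arm, 1000 runs, true ratio 1.00, an assumed 1 fall per 12 weeks, and an assumed dispersion of 1.5 treated as known. Unkept weeks were unrelated to falling.

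| Diary kept, FeetMe vs control | Follow-up offset: ratio, rejection at 5% | Weeks-kept offset: ratio, rejection at 5% |
|---|---|---|
| 90% vs 90% | 1.00, 4.9% | 1.00, 5.1% |
| 90% vs 70% | 1.28, 15.4% | 1.00, 4.4% |
| 70% vs 90% | 0.78, 15.2% | 1.00, 4.4% |

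**Check on the obvious remedy.** Using confirmed diary time as the only offset can fail in its own way. Suppose that patients record every fall but sometimes forget to tick an uneventful week, and that falls are infrequent. If 90% of fall-free weeks are ticked in the FeetMe arm and 70% in the control arm, exposure shrinks to about those shares. The rates rise by 1/0.90 = 1.11 and 1/0.70 = 1.43, and the ratio is multiplied by about 0.70/0.90 = 0.78. That is as large as the bias it was meant to remove, so confirmed time should not become the main offset.

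**The case against.** **In an event log, an empty week is correctly zero if no fall occurred.** Only omitted falls cause bias, and nothing stops a patient from entering an earlier fall later. This stands. The (1 − u) factor is an upper bound on the effect of unkept time that is unrelated to falling; it is not the expected result.

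**The direction is open.** A reader might infer that control patients keep the diary less well, so that a FeetMe benefit would be hidden. The documents do not support that. No section says that the APA calls prompt the falls diary, and none places the diary in the app. Control patients keep a second log, the physiotherapy tracking sheet (Section 8.8, Appendix F), and bring it to the same visits, which could make them the better recorders. This stands in full.

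**There is a second source.** Falls are adverse events of special interest, collected whatever their seriousness or relatedness (Section 8.9.3). Visit 3 asks about adverse events in both arms and is where the diary is transcribed (Section 7.4.3), so the site has an occasion to find unrecorded falls. This stands in part: the endpoint is defined on the diary, and no reconciliation is planned.

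**The exposure rule could be left to the statistical analysis plan.** Section 9 does leave derivation algorithms there. But no derivation can use diary coverage that was not collected, so this does not remove the point.

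**Conclusion.** The defect holds as a weakness of data collection. With this form, unkept diary time and fall-free time cannot be separated, and Sections 9.5.2 and 9.5.3 count both as observed exposure. Any fall omitted in such time lowers the rate.

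Its size is unknown. The factors 1.29 and 0.78 rest on assumed unkept shares of 10% and 30%, on equal fall frequency in kept and unkept time, and on the loss of every fall in unkept time. With equal omission in both arms the ratio is unbiased. The stronger reading, that the rate ratio will be biased or will be biased against FeetMe, is not supported.

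The reach is limited. Follow-up ends the exposure, so time after dropout is already excluded. The falls rate is a non-key secondary endpoint outside the hierarchical test of Section 9.2.2, so the primary and key secondary conclusions are unaffected. The change is still worth making, because it is cheap and unrecorded coverage cannot be recovered afterwards.

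**What to change.** 1. Add one dated line per week to Appendix G, with a choice between *no fall this week* and *falls entered above*.
2. Ask about falls and diary completion at the existing remote Visits 1 and 2 and at Visit 3, in the same way in both arms.
3. Reconcile the diary with falls reported as adverse events of special interest.
4. In Sections 9.5.2 and 9.5.3, keep the follow-up offset as the main analysis. Add a sensitivity analysis with the log of confirmed diary time as offset, counting only falls within confirmed time.

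The cost is a weekly tick for the patient, a short question at visits that already take place, and one more analysis. Confirmed-time exposure can itself be biased if ticking depends on having fallen, as the 0.78 in the check above shows. That is why it is proposed as a sensitivity analysis, and why the question at the visits matters as much as the tick.
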